#### **4.2. Treatment**

Data will be summarized according to sequence of treatment assignment and entry point of OLE:

- Placebo BID/Losmapimod 15 mg BID for subjects who completed 48 weeks of treatment in the placebo-controlled treatment period: This will include subjects who were assigned to Placebo at baseline and shifted to losmapimod 15 mg BID after Week 48 visit.
- Losmapimod 15 mg BID/Losmapimod 15 mg BID for subjects who completed 48 weeks of treatment in the placebo-controlled treatment period: This will include subjects who were assigned to losmapimod at baseline and shifted to losmapimod 15 mg BID after Week 48 visit.
- Placebo BID/Losmapimod 15 mg BID for subjects who completed 24 weeks of treatment in the placebo-controlled treatment period: This will include subjects who were assigned to Placebo at baseline and shifted to losmapimod 15 mg BID after Week 24 visit.
- Losmapimod 15 mg BID/Losmapimod 15 mg BID for subjects who completed 24 weeks of treatment in the placebo-controlled treatment period: This will include subjects who were assigned to losmapimod at baseline and shifted to losmapimod 15 mg BID after Week 24 visit.

#### **4.3. Handling of Missing Data**

All missing and partial data for the concomitant medications and adverse events will be handled as outlined in Sections [7.1](#) and [9.1](#), respectively.

In categorical summaries, a missing category will be included if and only if any data for the given endpoint is missing.

Missing values for other individual data points will remain as missing, unless otherwise, stated.

#### **4.4. Baseline, Study Day, and Change from Baseline Definitions**

Unless indicated otherwise, baseline will be defined as the last non-missing evaluation on or before the day of first dose of study drug in the placebo-controlled treatment period. If the last non-missing evaluation and the study drug administration occur on the same day, timing of the evaluation will be used to determine the pre- or post-dose. If timing is not available, the evaluation is considered pre- or post-dose based on the schedule of events for that assessment. For example, AEs and concomitant medication are considered post-baseline evaluations.

For the OLE baseline, it is defined as the last non-missing evaluation before the first dose of losmapimod in the OLE.

Relative study days will be calculated as:

$(\text{assessment date} - \text{first study drug administration date}) + 1$

if the assessment date is on the same day or after the first dosing date, otherwise:

$(\text{assessment date} - \text{first study drug administration date})$ .

Where applicable, study day relative to first dose of losmapimod will also be provided and this will be calculated as:

$(\text{assessment date} - \text{first losmapimod administration date}) + 1$

if the assessment date is on the same day or after the first dosing date, otherwise:

$(\text{assessment date} - \text{first losmapimod administration date})$ .

Both study days will be presented on all listings where appropriate.

Change from baseline will be computed as (post-baseline assessment value - baseline assessment value). Percent change from baseline will be computed as  $(\text{change from baseline value} / \text{baseline assessment value}) * 100$ . For the OLE visits, change from baseline will be computed based on both baseline assessment value, baseline in the placebo-controlled treatment period and baseline in OLE.

#### **4.5. Visit Windows**

In general, data for assessments that are collected by scheduled visits will be mapped to visits that appear in the schedule of assessments per the protocol using the actual study day of assessment. Data mapped to scheduled visits will include all data collected up to the

reporting cut-off date and may include withdrawal visits, unscheduled visits, end of treatment, and safety follow-up visits.

Visit windows will be continuous from the midpoint between two consecutive study visits and will be dependent on the schedule of assessments for each variable independently. For analysis that includes presentation of data in the placebo-controlled treatment period, there is an exception in the Week 16 analysis window. This has been extended to allow for potentially delayed visit due to COVID-19 pandemic. An example of the Vital Signs visit window is given in [Table 4-1](#). Visit windows for each variable will be constructed in the same manner.

**Table 4-1: Visit Windows**

Study Visit	Scheduled Day	Analysis Window
Baseline	1	<=1
Week 4	28	>1 to <=56
Week 12	84	>56 to <=98
Week 16	112	>98 to <=154
Week 24	168	>154 to <=210
Week 36	252	>210 to <=294
Week 48	336	>294 to <=378
Week 60	420	>378 to <=462
Week 72	504	>462 to <=546
Week 84	588	>546 to <=630
Week 96	672	>630 to <=714
Week 108	756	>714 to <=798
Week 120	840	>798 to <=882
Week 132	924	>882 to <=966
Week 144	1008	>966 to <=1050
Week 156	1092	>1050 to <=1134
Week 168	1176	>1134 to <=1218
Week 180	1260	>1218 to <=1302
Week 192	1344	>1302 to <=1386
Week 204	1428	>1386 to <=1470
Week 216	1512	>1470

#### **4.6. Multiple Values**

For summaries displayed by visit, multiple values for a given assessment within a time window will be handled as follows:

- Efficacy: The nearest non-missing value to the nominal timepoint will be assigned to the visit. If two values are equidistant from the nominal timepoint then the latest value will be selected.
- Safety: The earliest non-missing value within a visit window will be assigned to the visit.

For the PK and biomarker data, if the assay is believed to have failed for an assessment due to technical reasons, the sample will be re-run and the last/latest assessment date/time that is available will be used for the data analysis.

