3.1.2. Open-Label Extension

Once subjects reach Week 48, they will have the option to roll over into the OLE, with all subjects receiving 15 mg PO losmapimod tablets BID. Subjects who wish to roll over into the OLE must complete all procedures from the Week 48 end of placebo-controlled treatment period/start of OLE visit (Table 2).

Subjects will remain in the OLE until 90 days after commercial drug is available post regulatory approval or until the study is discontinued by the sponsor. All subjects who complete or discontinue from treatment will complete a safety follow-up visit 7 days (± 3 days) after the last dose of study drug.

During the OLE, subjects will attend clinic visits approximately every 12 weeks (Table 3). Study drug (open-label losmapimod) will be administered BID and should be taken with food.

Blood samples for PK (losmapimod concentration) will be collected after dosing at the Week 144 clinic visit, preferably ≥ 1 hour after dosing.

Safety and tolerability will be evaluated based on the assessment of AEs, AESIs, SAEs, laboratory tests, ECGs, vital signs, and physical examinations.

The full schedule of assessments for the OLE is provided in Table 3. Scheduled visits may be split over 2 days if required, with a maximum of 5 business days in between visits. Unscheduled visits may be performed if clinically indicated.

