- ^c Weight and height will be measured and BMI will be calculated once a year (ie, Week 72, Week 120, Week 168, Week 216, etc.). Weight and height will be measured with shoes off and preferably with the same balance.

- ^e Urine pregnancy tests will be performed for all female subjects of child-bearing potential before dispensation of study drug. If pregnancy is found, subjects must be terminated from the study effective immediately.
- ^f Vital signs (pulse rate, respiration rate, blood pressure, and temperature) will be collected after the subject has been seated or recumbent for at least 5 minutes and before any 12-lead ECG assessment or blood sampling is performed.
- ^g Physical examination at the safety follow-up visit includes an evaluation of body systems, including but not limited to the following: skin; head, eyes, ears, nose, and throat; respiratory system; cardiovascular system; abdomen (liver, spleen); lymph nodes; neurological system; and MSK system. Symptom-directed physical examinations can occur at any time during the study if triggered by adverse events or if deemed necessary by the investigator.
- ^h Twelve-lead ECGs will be performed after subjects have been recumbent for at least 5 minutes. Twelve-lead ECGs will be performed after the measurement of vital signs and before any procedures that may affect heart rate (eg, blood sampling).
- ⁱ Blood samples for PK will be collected after dosing at the Week 144 clinic visit only, preferably ≥ 1 hour after dosing.
- ^j The appropriate amount of study drug supply (losmapimod) will be given to the subject at each applicable visit to allow for dosing until their next scheduled study visit plus additional tablets to cover the visit window or additional study drug will be provided to the subject via a courier, as applicable. Study drug (losmapimod) will be taken twice daily and should be taken with food.
- ^k All medications taken within 28 days before screening through the safety follow-up visit will be recorded.

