## 7.2. Study Treatments

### 7.2.1. Extent of Exposure

The duration of exposure to losmapimod is the total number of days a subject is exposed to losmapimod; this duration is the interval from the first dose date of losmapimod to last dose date of losmapimod (ie, calculated as the date of last dose of losmapimod minus the date of first dose of losmapimod + 1). If the last dose date of losmapimod is missing, or if a subject is lost to follow-up, but the drug accountability log confirms that the subject has taken losmapimod, the visit date following the last completed drug accountability log will be used.

The exposure to losmapimod will also be characterized by cumulative dose, which is defined as the cumulative number of losmapimod tablets taken in the placebo-controlled treatment period and OLE.

The duration of exposure to losmapimod will be summarized for all subjects who entered OLE using summary statistics according to the sequence of actual treatment received in combination with entry point of OLE. For the Placebo BID/Losmapimod 15 mg BID column, only the duration of exposure while on losmapimod will be summarized. The duration of exposure will then be classified into the following categories: < 8 weeks, >= 8 weeks, >= 16 weeks, >= 24 weeks, >=36 weeks, >=48 weeks, >=60 weeks, >=72 weeks, >=84 weeks, >=96 weeks, >=108 weeks, >=120 weeks, >=132 weeks, >=144 weeks, >=156 weeks, >=168 weeks, >=180 weeks, >=192 weeks, >=204 weeks, and >=216 weeks and will be presented as the number and percentage of subjects in each duration category.

The total cumulative dose for losmapimod in mg will be defined as the total number of losmapimod tablets taken across all study days times 7.5 mg if 2 tablets were given while times 15 mg if 1 tablet was given. Average daily dose of losmapimod will be defined as cumulative dose of losmapimod divided by total days on losmapimod. The average daily dose and cumulative dose will be summarized using summary statistics according to the sequence of actual treatment received in combination with entry point of OLE. For the Placebo BID/Losmapimod 15 mg BID columns, only the cumulative dose and average daily dose for losmapimod will be summarized.

A summary of each subject's exposure to losmapimod will also be presented in a listing.

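### The open-ended Week 216 window, combined with the earliest-value rule, leaves later OLE values out of the by-visit safety summaries or labels them Week 216

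*SAP*

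**What the plan says.** SAP 4.5 assigns data to visits by actual study day. The general rule is "Visit windows will be continuous from the midpoint between two consecutive study visits", applied to each variable's own schedule. Table 4-1 is presented as the vital-signs example, and "Visit windows for each variable will be constructed in the same manner". One departure from the midpoints is declared: "there is an exception in the Week 16 analysis window". On coverage, the section says "Data mapped to scheduled visits will include all data collected up to the" reporting cut-off date, and it allows unscheduled, withdrawal and follow-up visits to be mapped.

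The last row of Table 4-1 is Week 216, scheduled Day 1512, with a window of any day after 1470. Every earlier post-baseline window has an upper limit.

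For several safety values in one window, SAP 4.6 says, for by-visit summaries: "The earliest non-missing value within a visit window will be assigned to the visit".

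On duration, Protocol 3.1.2 says "Subjects will remain in the OLE until 90 days after commercial drug is available post regulatory approval", or until the sponsor stops the study, with clinic visits about every 12 weeks. SAP 3.1 words the end point differently (study drug approval) but also gives no date. Protocol Table 3, footnote c, expects visits past Week 216: weight and height are taken "once a year (ie, Week 72, Week 120, Week 168, Week 216, etc". The exposure categories in SAP 7.2.1 end at ">=204 weeks, and >=216 weeks".

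**The concern.** Long-term safety is the primary objective of the OLE. Neither document defines an analysis visit after Week 216, so Weeks 228, 240, 252 and onward all fall in the Week 216 window. The earliest-value rule then keeps one of them per subject and assessment. The longest exposure is what drops out of the by-visit displays, although their titles say that they run to the data cut. Several of these tables (hematology, chemistry, urinalysis, vital signs and the two by-visit liver tables) are marked in SAP 14.4 for the Safety Review Committee. A subject who missed Week 216 contributes a value from a later visit under the Week 216 label.

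**Working it through.** **1. Reproduce Table 4-1.** Upper bound = (scheduled day of this visit + scheduled day of the next) / 2.

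- Week 4: (28 + 84)/2 = 56, as printed.
- Week 204: (1428 + 1512)/2 = 1470, as printed.
- Week 16: (112 + 168)/2 = 140, printed as 154. This is the declared COVID-19 exception.

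Of the 19 closed post-baseline bounds, 18 equal the midpoint and Week 16 is the exception. Only Week 216 is open.

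**2. Apply the same rule after Week 216.** Visits are 84 days apart, so Week 228 is Day 228 × 7 = 1596.

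- Week 216 upper bound: (1512 + 1596)/2 = 1554.
- Week 228: >1554 to <=1638. Week 240: >1638 to <=1722. And so on in 84-day steps.

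Values from visits after Week 216 are therefore misassigned only after Day 1554. Between Days 1471 and 1554 a value belongs to Week 216 under either reading.

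**3. Count what is lost.** If Week 216 was attended, its value is kept and (last week − 216)/12 later scheduled values are left out.

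| Followed to | Scheduled values after Day 1470 | Kept | Left out |
|---|---|---|---|
| Week 228 | 2 | 1 | 1 |
| Week 240 | 3 | 1 | 2 |
| Week 264 | 5 | 1 | 4 |
| Week 288 | 7 | 1 | 6 |

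Missed visits change this little. Suppose each visit from Week 216 to Week 264 is missed independently with probability p (an assumption; the documents give no rate). The expected number of post-216 values is 4(1 − p). The chance that one of them is kept under the Week 216 label is p(1 − p⁴). The mislabelled share is p(1 − p⁴)/[4(1 − p)]: 1.3%, 2.8% and 6.2% for p = 5%, 10% and 20%. The remaining 98.7%, 97.2% and 93.8% are left out.

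**4. When it starts.** Protocol 3.1.1 states that on 10 April 2020 enrolment was complete and 12 subjects had rolled over at Week 24.

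- Last enrolled, assuming Day 1 no later than 10 April 2020: Day 1554 = that date + 1553 days = 11 July 2024.
- The 12 early rollovers, assuming a Week 24 visit at the early edge of its window (Day 168 − 5 = 163) by 10 April 2020: Day 1 no later than 31 October 2019, so Day 1554 falls by 31 January 2024.

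**5. Which outputs use the rule.**

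- Affected: hematology, chemistry, urinalysis, vital signs and ECG summarized by visit (SAP 9.2, 9.3, 9.5).
- Not affected: AE tables; listings, which show all repeat and unscheduled values (SAP 4); shift tables built on the post-baseline minimum and maximum (SAP 9.2.1, 9.2.2); maximum on-treatment QTcF categories (SAP 9.5).
- Unclear: Tables 14.3.4.2.3 (notable liver results) and 14.3.4.2.4 (DILI). SAP 9.2.2 counts a notable abnormality if a value qualifies on any occasion during treatment, which needs all values. The table titles in SAP 14.4 specify by visit, which brings in SAP 4.6.
- By-visit efficacy is little affected. It takes the value nearest the nominal day, and version 5.0 stopped collecting it.

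**The case against.** The strongest reply is that Table 4-1 is only an example. The governing text maps data to the protocol's scheduled visits with midpoint bounds, and version 5.0 continues quarterly visits, so a programmer applying that text to Week 228 would arrive at Day 1554 unaided. That is a fair account of what was probably meant. It does not cure the problem: the printed last row states an open window, other variables are to copy the construction, and the section declares its Week 16 exception but says nothing about Week 216. Followed literally, the table gives the wrong result.

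The second reply is that late safety signals still surface, and this stands. A reader might infer that all safety data after Week 216 disappear, or that a late liver case would be hidden from the Safety Review Committee. The documents do not support either. Potential DILI is an adverse event of special interest counted in the AE summary (SAP 9.1). The chemistry shift table, the chemistry listing and the overall TEAE tables are all marked for the committee, and subjects with DILI have their own listing (16.2.8.2.2).

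A reader might also infer that the exposure categories lose subjects. They do not: the categories are cumulative, so everyone beyond 216 weeks is counted, and the summary statistics include the maximum.

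Finally, the data-cut date is left blank throughout SAP 14.4, so whether the problem occurs at all depends on when the cut is made. That also stands.

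**Conclusion.** The defect is real but limited. As written, once the data cut falls after Week 228 visits, the by-visit summaries of hematology, chemistry, urinalysis, vital signs and ECG keep one value per subject after Day 1470. Later values are left out if Week 216 was attended; if not, the first later value appears as Week 216. The two by-visit liver tables share the problem only if SAP 4.6 governs them, and SAP 9.2.2 and the table titles need to be reconciled on that.

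The loss is 2, 4 or 6 scheduled visits per subject followed to Week 240, 264 or 288 with Week 216 attended, and none if the cut precedes Week 228. These are scenarios; the documents do not say how far follow-up went. The dates rest on the Day 1 assumptions above and are latest dates for subjects still in the study. It would be wrong to date the loss from Day 1470, which is where the Week 216 window opens and is 84 days before any later visit is misassigned.

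**What to change.** - In Table 4-1, close Week 216 at >1470 to <=1554 for variables assessed every 12 weeks. Add Week 228 (>1554 to <=1638), Week 240 (>1638 to <=1722) and further 84-day windows to the data cut.
- For less frequent assessments, use their own midpoints. For annual weight and BMI, the visit after Week 216 is Week 264 (Day 1848), so Week 216 closes at (1512 + 1848)/2 = Day 1680.
- State in SAP 9.2.2 that notable-liver and DILI counts use all on-treatment values, and align the by-visit titles of Tables 14.3.4.2.3 and 14.3.4.2.4 with that.
- Optionally, extend the exposure categories past 216 weeks. This adds detail only.

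The cost is a few table rows and a programming parameter. The downside is longer tables with small numbers at late visits.

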#### **4.7. Subgroup**

A subgroup analysis will be performed for the following subsets at baseline:

- 1) Sex (Male, Female)
- 2) Age (<50 years old and  $\geq$ 50 years old)

Endpoints for which the subgroup analysis will be performed are indicated in subsequent sections.

#### **4.8. Sample Size**

The sample size for OLE is determined by the number of subjects anticipated to roll over from the placebo-controlled treatment period. A total of 80 subjects have been enrolled in the placebo-controlled treatment period which is 4 subjects higher than the planned sample size of 76 subjects.

#### **4.9. Randomization and Blinding**

This non-randomized OLE includes subjects who previously completed the placebo-controlled treatment period part. No blinding will be performed (subjects will receive open-label losmapimod); however, subjects will remain blinded to their original treatment assignment from the placebo-controlled treatment period for the duration of the study. The Sponsor and/or its designee may be unblinded after all subjects have completed the Week 48 visit (or have discontinued) and the database from the placebo-controlled treatment period has been locked for statistical analyses. The █ Biostatistics and Programming will be unblinded after the data for the placebo-controlled treatment period has been locked.

## **4.10. Analysis Set**

### **4.10.1. Open-label Analysis Set**

The open-label analysis set will consist of all subjects who complete 24 or 48 weeks of treatment in the placebo-controlled treatment period and receive at least 1 dose of open-label losmapimod in the OLE.

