4.2.2. Handling of Withdrawals

Subjects are free to withdraw from the study or study treatment at any time upon request. Subject participation in the study may be stopped at any time at the discretion of the investigator or at the request of the sponsor.

Subjects who discontinue study treatment or active participation in the study will no longer receive study drug. When a subject withdraws from the study treatment or active participation in the study, the reason(s) for withdrawal shall be recorded by the investigator on the relevant page of the electronic case report form (eCRF).

If a subject prematurely discontinues study treatment, they will be encouraged to remain in the study and continue with all other aspects of the study.

If a subject decides to prematurely discontinue study treatment and not continue with all other aspects of the study, they will be considered to have withdrawn from the study. If a subject withdraws from the study, they will be asked to complete the early termination (ET) visit as soon as possible after the decision to terminate study participation and to complete the safety follow-up visit 7 (± 3) days after their last dose of study drug. If the ET visit will be scheduled more than 7 days after the last dose of study drug, the safety follow-up and ET visits may be combined, with no duplication of assessments required.

Subjects who fail to return for final assessments will be contacted by the site in an attempt to have them comply with the protocol. In the case of subjects being lost to follow-up, at least 3 documented attempts to contact the subject must be made.

It is vital to obtain follow-up data on any subject withdrawn because of an AE or SAE. In every case, efforts must be made to undertake protocol-specified, safety, follow-up procedures.

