7.4. ANALYSIS SETS

The following analysis sets will be used in the statistical analyses.

Full analysis set (FAS): The FAS will consist of all subjects who are randomly assigned to receive double-blind study drug in the placebo-controlled treatment period. All analyses using the FAS will group subjects according to randomized treatment. The FAS is the main analysis population for key study endpoints (Section 7.6.1). For the secondary and exploratory endpoints, subjects who already transitioned into the OLE portion under protocol version 3.0 will be analyzed as randomized, in this analysis population.

Per-protocol set (PPS): The PPS will consist of all FAS subjects who fulfill all inclusion/exclusion criteria and do not have any significant protocol deviations. All analyses using the PPS will group subjects according to randomized treatment. PPS analyses will be conducted for key study endpoints (Section 7.6.1) to assess robustness of key study inferences.

Safety analysis set: The safety analysis set will consist of all subjects who receive any study drug. All analyses using the safety analysis set will group subjects according to treatment actually received.

Pharmacokinetic analysis set: The PK analysis set will consist of all subjects who receive at least 1 dose of losmapimod and have evaluable PK data for losmapimod.

Pharmacodynamic analysis set: The PD analysis set will consist of all subjects who receive at least 1 dose of losmapimod and have evaluable PD data for losmapimod.

Open-label losmapimod (Pre-COVID-19) analysis set: This analysis set will consist of subjects who were already transitioned into open-label losmapimod under version 3.0 of the protocol. This analysis set will be used for sensitivity analysis, to assess secondary/exploratory endpoints in this subset of subjects.

Open-label analysis set: The open-label analysis set will consist of all subjects who complete 24 weeks of treatment in the placebo-controlled treatment period and receive at least 1 dose of open-label losmapimod in the OLE. Safety and efficacy analyses in the OLE will be based on this analysis set.

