7.6.6. Safety Analyses

Safety data in the placebo-controlled treatment period will be analyzed using the safety analysis set and summarized by treatment group and visit (if applicable) using descriptive statistics. Safety data in the OLE will be analyzed using the open-label analysis set.

Treatment-emergent AEs will be summarized by MedDRA system organ class and preferred term; separate summaries will be produced for treatment-related AEs, AESIs, SAEs, and discontinuations due to AEs. Laboratory tests, vital signs, findings from physical examinations, and ECGs will be summarized for changes over time during treatment using descriptive statistics.

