### 4.1. Analysis Periods

For the purposes of efficacy and safety data analysis, and for reporting, two analysis periods for post baseline data are defined: placebo-controlled treatment period and OLE. The placebo-controlled treatment period encompasses data through Week 48 or Week 24 for subjects who prior to the COVID-19 pandemic had the option to roll over into the OLE at Week 24. The OLE encompasses all losmapimod data starting a day after the Week 48 visit or Week 24 visit for subjects who prior to the COVID-19 pandemic had the option to roll over into the OLE at Week 24. The duration of OLE is defined for each subject as the time after completion of the Week 48 or Week 24 for subjects who prior to the COVID-19

pandemic had the option to roll over into the OLE at Week 24 through completion of the safety follow-up after the end of treatment or discontinuation of the study.

In addition, a supplementary analysis period will be considered which is the losmapimod exposure period that encompasses all losmapimod exposure data, irrespective of when the losmapimod exposure starts (i.e., baseline or OLE).

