14.3.1.5.2	Table 14.3.1.5.2 Treatment-Emergent Adverse Events Leading to Treatment Discontinuation by System Organ Class and Preferred Term During Open-label Extension through Data-Cut Date (ddmmmyyyy) Open-label Analysis Set	Open-label Analysis Set	R	9.1.5	Safety	

14.3.1.5.3	Table 14.3.1.5.3 Treatment-Emergent Adverse Events Leading to Treatment Discontinuation by System Organ Class and Preferred Term During Placebo-Controlled Treatment Period Open-label Analysis Set	Open-label Analysis Set	R	9.1.5	Safety	
14.3.1.6.1	Table 14.3.1.6.1 Treatment-Emergent Adverse Events Leading to Study Withdrawal by System Organ Class and Preferred Term through Data-Cut Date (ddmmmyyyy) Open-label Analysis Set	Open-label Analysis Set	R	9.1.6	Safety	
14.3.1.6.2	Table 14.3.1.6.2 Treatment-Emergent Adverse Events Leading to Study Withdrawal by System Organ Class and Preferred Term During Open-label Extension through Data-Cut Date (ddmmmyyyy) Open-label Analysis Set	Open-label Analysis Set	R	9.1.6	Safety	
14.3.1.6.3	Table 14.3.1.6.3 Treatment-Emergent Adverse Events Leading to Study Withdrawal by System Organ Class and Preferred Term During Placebo-Controlled Treatment Period Open-label Analysis Set	Open-label Analysis Set	R	9.1.6	Safety	
14.3.2.1.1	Table 14.3.2.1.1 Serious Treatment-Emergent Adverse Events by System Organ Class and Preferred Term through Data-Cut Date (ddmmmyyyy) Open-label Analysis Set	Open-label Analysis Set	R	9.1.4	Safety	Y
14.3.2.1.2	Table 14.3.2.1.2 Serious Treatment-Emergent Adverse Events by System Organ Class and Preferred Term During Open-label Extension through Data-Cut Date (ddmmmyyyy) Open-label Analysis Set	Open-label Analysis Set	R	9.1.4	Safety	Y
14.3.2.1.3	Table 14.3.2.1.3 Serious Treatment-Emergent Adverse Events by System Organ Class and Preferred Term During Placebo-Controlled Treatment Period Open-label Analysis Set	Open-label Analysis Set	R	9.1.4	Safety	
14.3.2.2.1	Table 14.3.2.2.1 Adverse Events Leading to Death by System Organ Class and Preferred Term through Data-Cut Date (ddmmmyyyy) Open-label Analysis Set	Open-label Analysis Set	R	9.1.7	Safety	
14.3.4.1.1	Table 14.3.4.1.1 Change from Baseline in Hematology through Data-Cut Date (ddmmmyyyy) Open-label Analysis Set	Open-label Analysis Set	U	9.2.1	Safety	Y

14.3.4.1.2	Table 14.3.4.1.2 Shift from Baseline in Hematology through Data-Cut Date (ddmmmyyyy) Open-label Analysis Set	Open-label Analysis Set	U	9.2.1	Safety	Y

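### The OLE SAP runs its controlled-period and cumulative safety tables on the rollover set, which leaves out losmapimod-randomised subjects who stopped during the controlled period; this departure from the protocol is not declared

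*SAP*

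**What the plan says.** SAP 4.10.1 is the only analysis-set definition in the OLE SAP. Each member must "complete 24 or 48 weeks of treatment in the placebo-controlled treatment period and receive at least 1 dose of open-label losmapimod in the OLE". Every table in SAP 14.4 names this set. Besides the tables for the OLE period, the list holds two other families of AE table:

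- **Controlled period.** Tables 14.3.1.1.3 to 14.3.1.6.3 and 14.3.2.1.3. Table 14.3.1.5.3 is titled "Treatment-Emergent Adverse Events Leading to Treatment Discontinuation by System Organ Class and Preferred Term During Placebo-Controlled Treatment Period Open-label Analysis Set" and Table 14.3.1.6.3 "Treatment-Emergent Adverse Events Leading to Study Withdrawal by System Organ Class and Preferred Term During Placebo-Controlled Treatment Period Open-label Analysis Set".
- **Cumulative through the data cut.** These include overall TEAEs (14.3.1.1.1), AE discontinuations (14.3.1.5.1), serious TEAEs (14.3.2.1.1) and deaths (14.3.2.2.1). The potential-DILI table (14.3.4.2.4) is cumulative too.

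The protocol treats the controlled period differently. Section 7.6.6 says: "Safety data in the placebo-controlled treatment period will be analyzed using the safety analysis set". Section 7.4 defines that set: "The safety analysis set will consist of all subjects who receive any study drug". Section 7.6.6 assigns only OLE safety to the open-label set.

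SAP 4.1 also defines a supplementary period, a "losmapimod exposure period that encompasses all losmapimod exposure data, irrespective of when the losmapimod exposure starts". In the 14.4 list, the treatment-duration and compliance tables carry that label (14.1.6.1 and 14.1.6.2). The first annualised-change analysis in SAP 8.1 also uses on-losmapimod data from both periods. No AE table is built on it.

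**The concern.** The primary OLE objective is the safety and tolerability of long-term losmapimod. A table of adverse events that led subjects to stop in a given period is informative only if the subjects who stopped can appear in it. Here membership requires that they did not stop.

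The cumulative tables have the same gap in a less visible form. SAP 9.1 presents its overview as covering the whole study, yet a subject randomised to losmapimod who stopped for an adverse event in the controlled period, or died then, is absent. Potential DILI is the protocol's named event of special interest (6.2.1.3). A subject whose losmapimod was stopped for it in the controlled period would not appear in the cumulative DILI table. The cumulative losmapimod discontinuation rate is therefore biased downward.

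**Working it through.** **Set logic**

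1. Membership needs completed controlled treatment and at least one open-label dose (SAP 4.10.1).
2. Protocol 4.2.2: "Subjects who discontinue study treatment or active participation in the study will no longer receive study drug". A subject who stops in the controlled period therefore cannot have an open-label dose.
3. So no such subject is in the set, and Tables 14.3.1.5.3 and 14.3.1.6.3 have an expected count of about zero in both arms, whatever the true rate. The only possible entry is an event that began in the controlled period and led to stopping later.
4. The open-label-dose condition alone produces this result. Removing the completion condition would not fill the tables.
5. SAP section 11 lists two modifications: interim analyses during the OLE, and the addition of 48-week completers to the open-label set. It does not list the use of this set for controlled-period safety.
6. SAP 9.1 counts TEAEs from the first dose of study drug, and SAP section 1 lets that term mean losmapimod and/or placebo. The cumulative Placebo/Losmapimod columns therefore mix placebo time with losmapimod time. The OLE-period tables isolate losmapimod time for those subjects but not for the losmapimod-first sequences. No planned AE table counts all losmapimod exposure from first losmapimod dose.

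**Size**

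The plan states no discontinuation rate or count, so there is no figure of its own to reproduce. From the documents: 80 enrolled, 1:1 allocation. Assumptions:

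- 40 subjects per arm.
- A 48-week AE-discontinuation rate d on losmapimod, the same in both sequences, ranging from 2.5% to 15%.
- No other losses, and all placebo subjects roll over.
- Everyone treated as rolling over at Week 48.

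Over the first 48 weeks of losmapimod, the true rate among all exposed is (40d + 40d)/80 = d. In the open-label set, the 40d losmapimod-first stoppers are missing from numerator and denominator, so the rate shown is 40d/(40(1 − d) + 40), and its ratio to the true rate is 1/(2 − d).

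| d | Losmapimod-arm AE stops in controlled period: safety set / open-label set | First-48-week rate shown in open-label set | Share of true rate |
|---|---|---|---|
| 2.5% | 1 / about 0 | 1/79 = 1.3% | 51% |
| 5% | 2 / about 0 | 2/78 = 2.6% | 51% |
| 10% | 4 / about 0 | 4/76 = 5.3% | 53% |
| 15% | 6 / about 0 | 6/74 = 8.1% | 54% |

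If a fraction q of the placebo arm does not roll over, the share of the true rate becomes 40(1 − q)/(40(1 − d) + 40(1 − q)). This is also the placebo-first share of the set. For q from 0 to 10% it runs from 36/75 = 48% (d = 2.5%, q = 10%) to 40/74 = 54% (d = 15%, q = 0).

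Twelve subjects rolled over at Week 24 (protocol 3.1.1). Stops after Week 24 among the losmapimod-first subjects of that group would be captured, so the true shortfall would be somewhat smaller than the table shows.

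**The case against.** The strongest reply is that nothing is lost from the trial. The protocol gives the controlled period its own safety set, and SAP section 1 says a separate SAP was written for that period. The controlled-period discontinuations should be reported there. The protocol itself prescribes the open-label set for OLE-period safety, and every affected table carries the set's name in its title. All of this stands, and the OLE-period tables need no change. It does not rescue two tables that cannot show what their titles describe, or cumulative tables that start at first dose but omit early stoppers. The controlled-period SAP was not available, so its tables could not be checked.

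Two stronger readings are tempting, and the documents do not support them.

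- **That long-term safety is shown only in subjects who tolerated losmapimod.** SAP 4.2 includes two Placebo/Losmapimod sequences. Those subjects enter losmapimod-naive, and their early losmapimod stops appear in the OLE-period tables (14.3.1.5.2 and 14.3.1.6.2). Under the assumptions above they make up about half of the set. The selection on losmapimod tolerance applies to the Losmapimod/Losmapimod sequences only.
- **That the completion clause drops subjects who stopped blinded drug, stayed in the study and then took open-label drug at Week 48.** Protocol 4.2.2 does say "If a subject prematurely discontinues study treatment, they will be encouraged to remain in the study", but this concerns aspects of the study other than treatment, and the same section gives discontinuers no further study drug. SAP 4.9 also describes the OLE as including subjects who completed the controlled part. Protocol 3.1.2, which speaks of reaching Week 48, does not clearly override this.

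**Conclusion.** The point holds in this form. The controlled-period tables depart from protocol 7.6.6 without declaration in SAP section 11. The controlled-period discontinuation and withdrawal tables are all but empty by construction; this follows from the definitions alone and needs no numerical assumption. The cumulative TEAE, serious TEAE, death and DILI tables omit every losmapimod-randomised subject who stopped in the controlled period, and no AE table in this SAP covers all losmapimod exposure from first losmapimod dose.

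The size is illustrative only: about 51-54% of the true first-48-week AE-discontinuation rate is shown (48-54% if up to 10% of placebo subjects do not roll over). It rests on the assumed arm size, the assumed range of d, and equal rates in both sequences. The other controlled-period tables (TEAEs by class, severity, relationship and seriousness) are incomplete, not empty.

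**What to change.** 1. Run the controlled-period TEAE tables (14.3.1.1.3 to 14.3.1.6.3, and 14.3.2.1.3) on the protocol's safety analysis set, or delete them and cross-refer to the controlled-period report.
2. Add TEAE, serious TEAE, AE-discontinuation and potential-DILI tables for the losmapimod exposure period of SAP 4.1, in all subjects with at least one dose of losmapimod in either period, counted from first losmapimod dose.
3. Keep the open-label set for the OLE-period tables. If any controlled-period table stays on it, list that in SAP section 11.

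The cost is SAP wording and a few additional or re-run tables on data already held. Reported AE-discontinuation rates may rise.
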